1. PROTOCOL SYNOPSIS Study Centers	Approximately 50 sites (multiple countries)	Approximately 75 sites (multiple countries)	To increase number of sites to account for increased number of subjects
1. PROTOCOL SYNOPSIS Number of subjects	Initially at least 20 subjects taking phenytoin and at least 20 subjects taking phenobarbital; followed by an additional approximately 450 subjects taking AEDs other than phenytoin or phenobarbital, at a time to be determined by the Sponsor, to further evaluate long term safety.	At least 20 subjects taking phenytoin and at least 20 subjects taking phenobarbital and approximately an additional 700 subjects taking AEDs other than phenytoin or phenobarbital, to further evaluate long term safety.	To increase number of subjects to be enrolled in the study
1. PROTOCOL SYNOPSIS Design and methodology	Subjects on concomitant AEDs other than phenytoin or phenobarbital: The titration phase for subjects on stable doses of other concomitant AEDs will be 4 weeks. Increasing doses of YKP3089 will be administered (50, 100, 150 and 200mg/day) at 1-week intervals. The investigator may add, remove, or adjust the dosage of concomitant AEDs, as clinically indicated in this group of subjects. Monotherapy with YKP3089 will not be allowed.	Subjects on concomitant AEDs other than phenytoin or phenobarbital: The titration phase for subjects on stable doses of other concomitant AEDs will be 8 weeks. Increasing doses of YKP3089 will be administered (50, 100, 150 and 200mg/day) at 2-week intervals. The investigator may add, remove, or adjust the dosage of concomitant AEDs, as clinically indicated in this group of subjects. Monotherapy with YKP3089 will not be allowed.	A recent aggregate analysis revealed that the rate of rash/hypersensitivity reactions was lowest when the rate of titration was at 50mg every two weeks
1. PROTOCOL SYNOPSIS Statistics and analyses	The results of the open-label extension will be reported using summary tables, figures, and data listings. Summaries will be presented for demographic information and safety information only.	The results of the open-label extension will be reported using summary tables, figures, and data listings. Summaries will be presented for demographic information and safety information only.	To correct typographical error
3. STUDY ASSESSMENTS Table 1	Column headers were separate for phenytoin/phenobarbital vs other concomitant AEDs	All subjects have same titration rate with a single set of headers	All subjects will have the same titration rate
4.4.3 Clinical Safety and Efficacy	Cumulatively, approximately 800 subjects have been exposed to YKP3089 in a total of 12 Phase 1 and 3 Phase 2 clinical studies.	Cumulatively, 953 subjects have been exposed to YKP3089 in a total of 14 Phase 1 and 3 Phase 2 clinical studies.	To provide updated exposure, safety and efficacy data

Amendment 2

Reasons for Amendment

1. To increase number of subjects to be enrolled in the study
2. To reduce the initial dose of YKP3089
3. To slow the rate of titration of YKP3089
4. To update the exclusion criteria
5. To provide updated YKP3089 exposure, safety and efficacy data in the introduction
6. To increase the frequency of visits and evaluations during the first 16 weeks of therapy with YKP3089
7. To update the skin/hypersensitivity safety assessments
8. To provide information for two new dosage strengths
9. To update the risk benefit profile in the introduction
10. To make administrative changes

Amendment 2 Summary of Changes

Section	Old Text	Amended Text	Rationale
1. PROTOCOL SYNOPSIS Study Center(s)	Approximately 75 sites (multiple countries)	Approximately 50-100 sites (multiple countries)	To increase number of sites to account for increased number of subjects
1. PROTOCOL SYNOPSIS Number of subjects	At least 20 subjects taking phenytoin and at least 20 subjects taking phenobarbital and approximately an additional 700 subjects taking AEDs other than phenytoin or phenobarbital, to further evaluate long term safety.	At least 20 subjects taking phenytoin and at least 20 subjects taking phenobarbital. Additional subjects taking AEDs other than phenytoin or phenobarbital, will be enrolled in order to expose a total of at least 1,000 subjects for at least 6 months.	To increase number of subjects to be enrolled in the study
1. PROTOCOL SYNOPSIS Design and methodology	
The study will consist of a screening period, open-label titration phase, open label maintenance phase and a taper and follow up.
 
Screening period
 
The screening period for subjects on stable doses of phenytoin or stable doses of phenobarbital or stable doses of other concomitant AEDs will be up to 21 days.
 
Titration phase
 
Subjects on phenytoin or phenobarbital:
 
The titration phase for subjects on stable doses of phenytoin or stable doses of phenobarbital will be 8 weeks. Increasing doses of YKP3089 will be administered (50, 100, 150 and 200mg/day) at 2-week intervals. Sparse sampling of phenytoin, phenobarbital and YKP3089 plasma levels will be
	
The study will consist of a screening period, a 12 week open-label titration phase, an open label maintenance phase and a taper and follow up. Clinic visits during the first 16 weeks of therapy will be every two weeks with a telephone contact between each visit. At each visit during the first 16 weeks physical exams to evaluate signs of hypersensitivity will be performed and laboratory evaluations will be obtained.
 
Screening period
 
The screening period for subjects on stable doses of phenytoin or stable doses of phenobarbital or stable doses of other concomitant AEDs will be up to 21 days.
 
Titration phase
 
Subjects on phenytoin or phenobarbital:
 
The titration phase for subjects on stable doses of phenytoin or stable doses of phenobarbital will be 12 weeks. Increasing doses of YKP3089 will be administered (12.5, 25, 50, 100, 150 and 200mg/day) at 2-week intervals. Sparse sampling of phenytoin, phenobarbital and YKP3089
	
To reduce the rate of DRESS incidence by lowering initial dose of YKP3089 and slowing the rate of titration

Amendment 3

Reasons for Amendment

1. To allow subjects to increase the target dose up to 400 mg/day
2. Minor administrative changes

Amendment 3 Summary of Changes

Section	Old Text	Amended Text	Rationale

1. PROTOCOL SYNOPSIS Open Label Maintenance Phase Subjects on phenytoin or phenobarbital
	
If the investigator feels that a subject requires a dose that is lower than 200 mg/day, the dose can be reduced to a minimum of 50 mg/day once the target dose of 200 mg/day was reached. The dose adjustments may occur in weekly increments of 100-mg/day or 50-mg/day. However, the rate of change may be more rapid or slow as clinically indicated. The investigator may add, remove, or adjust the dosage of concomitant AEDs, as clinically indicated. Monotherapy with YKP3089 will not be allowed.
	
If the investigator feels that a subject requires a dose that is higher than 200 mg/day, the dose can be increased to a maximum of 400 mg/day once the target dose of 200 mg/day was reached. The upward dose adjustments should occur every other week in increments of 50-mg/day. If the investigator feels that a subject requires a dose that is lower than 200 mg/day, the dose can be reduced to a minimum of 50 mg/day once the target dose of 200 mg/day was reached. The downward dose adjustments may occur weekly by 100-mg/day or 50-mg/day. However, the downward rate of change may be more rapid or slow as clinically indicated. The investigator may add, remove, or adjust the dosage of concomitant AEDs, as clinically indicated. Monotherapy with YKP3089 will not be allowed.
	
To increase to a maximum of 400mg/day


PROTOCOL SYNOPSIS Open Label Maintenance Phase Subjects on concomitant AEDs other than phenytoin or phenobarbital
	
If the investigator feels that a subject requires a dose that is lower than 200 mg/day, the dose can be reduced to a minimum of 50 mg/day once the target dose of 200 mg/day was reached. The dose adjustments may occur in weekly increments of 100-mg/day or 50-mg/day. However, the rate of change may be more rapid or slow as clinically indicated.
	
For subjects taking other concomitant AEDs, the initial target dose will be 200 mg/day. If the investigator feels that a subject requires a dose that is higher than 200 mg/day, the dose can be increased to a maximum of 400 mg/day once the target dose of 200 mg/day was reached. The upward dose adjustments should occur every other week in increments of 50-mg/day. If the investigator feels that a subject requires a dose that is lower than 200 mg/day, the dose can be reduced to a minimum of 50 mg/day once the target dose of 200 mg/day was reached. The downward dose adjustments may occur weekly by 100-mg/day or 50-mg/day. However, the downward rate of change may be more rapid or slow as clinically indicated.
	
To increase to a maximum of 400mg/day

Section 4.5 Rationale Section 4.5.2.Dose Justification
		
After reaching a target dose of 200mg, all subjects will be allowed to titrate up to a maximum dose of 400mg/day of YKP3089. A maximum dose of 400mg/day is justified by the additional efficacy
	
To increase to a maximum of 400mg/day

Amendment 4

Reasons for Amendment

1. To update inclusion and exclusion criteria to more effectively screen patients for a safety study
2. To update Birth Control Methods Allowable for Enrollment of Subjects
3. To add vital signs details to the Study Assessment table
4. To update screening number assignment
5. To clarify prohibited medications or devices
6. To clarify pharmacokinetics sampling
7. To update Medical Monitor contact information
8. Minor administrative and editorial changes

Amendment 4 Summary of Changes

Section	Old Text	Amended Text	Rationale
3. STUDY ASSESSEMENT NTS Table 1. Study Assessment Flow Chart	b. Vital signs include blood pressure, and heart rate (supine for 5 minutes).	b. Vital signs include blood pressure, heart rate (supine for 5 minutes), temperature, and respiratory rate.	To update vital sign details in the study assessment table
3. STUDY ASSESSEMENT NTS Table 1. Study Assessment Flow Chart	i. Two blood samples will be collected for the determination of YKP3089 plasma levels: the first one will be collected upon subjects' arrival to the study unit; the second one should be collected within 2 to 4 hours after the first blood draw. Collect at visit 8 and/or 9 depending on stability of dosing (doses must be stable for 2 weeks prior to these visits) of all concomitant AEDs including oxcarbazepine, topiramate, lamotrigine, lacosamide, clobazam, perampanel, levetiracetam, phenytoin and phenobarbital and YKP3089.	i. Two blood samples will be collected for the determination of YKP3089 plasma levels: For patients that are taking YKP3089 in the morning and coming into the visits in the morning, the first blood draw will be collected upon subjects' arrival to the study unit; the second blood draw should be collected within 30 minutes to 2 hours after the medication is taken. Collect at visit 8 and/or 9 depending on stability of dosing (doses must be stable for 2 weeks prior to these visits) of all concomitant AEDs including oxcarbazepine, topiramate, lamotrigine, lacosamide, clobazam, perampanel, levetiracetam, phenytoin and phenobarbital and YKP3089. YKP3089 PK draw is applicable for subjects on phenytoin and phenobarbital globally and all subjects at US sites.	To clarify pharmacokinetics sampling
3. STUDY ASSESSEMENT NTS Table 1. Study Assessment Flow Chart	j. At Visit 2, a single trough level of phenytoin or phenobarbital will be obtained. At visits 4, 5, 6, 7 and 8 two blood samples will be collected for the determination of phenobarbital and phenytoin plasma levels: the first one will be collected upon subjects' arrival to the study unit; the second one should be collected within 2 to 4 hours after the first blood draw.	j. At Visit 2, a single trough level of phenytoin or phenobarbital will be obtained. At visits 4, 5, 6, 7 and 8 two blood samples will be collected for the determination of phenobarbital and phenytoin plasma levels: For subjects that are taking phenytoin or phenobarbital in the morning and coming into the visits in the morning, the first blood draw will be collected upon subjects' arrival to the study unit; the second blood draw should be collected within 2 to 4 hours after the medication is taken.	To clarify pharmacokinetics sampling

1 PROTOCOL SYNOPSIS

Name of company	SK Life Science Inc
Title of study	An Open Label, Multicenter, Safety and Pharmacokinetic Study of YKP3089 as Adjunctive Therapy in Subjects with Partial Onset Seizures
Protocol number	YKP3089C021
Phase of development	Phase 3
Study duration	After 12 months of participation in the study, subjects will be evaluated for treatment response. Those who are benefiting from treatment with YKP3089 may continue use of the drug at the discretion of the investigator, until development is stopped by SK Life Science Inc or the product is approved for marketing, or anytime at the discretion of SK Life Science Inc.
Indication	Partial-onset epilepsy
Study center(s)	Approximately 80-110 sites (multiple countries)
Number of subjects	At least 20 subjects taking phenytoin and at least 20 subjects taking phenobarbital. Additional subjects taking AEDs other than phenytoin or phenobarbital, will be enrolled in order to expose a total of at least 1,000 subjects for at least 6 months.
Objectives	
The objective is to evaluate the safety and pharmacokinetics of YKP3089 and concomitant AEDs when administered as adjunctive therapy for the treatment of partial seizures. The evaluations will include:
 
 1. Phenytoin-YKP3089 interaction 2. Phenobarbital-YKP3089 interaction 3. Long term safety of YKP3089 as adjunctive therapy in partial onset seizures 4. Population pharmacokinetics of YKP3089 and concomitant AEDs.
Inclusion and exclusion criteria	
Subjects to be enrolled in the study include:
 
 1. Subjects on stable doses of phenytoin 2. Subjects on stable doses of phenobarbital 3. Subjects on stable doses of other concomitant AEDs 
Subjects who meet all inclusion and no exclusion criteria listed in Section 7.3 and Section 7.4 of the protocol are eligible to enroll.

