YKP3089 dose (mg/day)					
Week 1 & 2	Week 3 & 4	Week 5 & 6	Week 7 & 8	Week 9 & 10	Week 11 & 12
12.5	25	50	100	150	200

Prior to initiating YKP3089, subjects at US sites only will have trough concomitant AED levels (oxcarbazepine, topiramate, lamotrigine, lacosamide, clobazam, perampanel and levetiracetam only) drawn at Visit 2. Sites must instruct the subject and schedule the visit accordingly to obtain a trough level. Also the blood must be collected before first dose of YKP3089. To improve tolerability, the investigator may instruct the subject to take the dose of YKP3089 in the evening. The investigator may add, remove, or adjust the dosage of any concomitant AEDs, as clinically indicated (see [Table 8](#) below). Monotherapy with YKP3089 will not be allowed. If clinically indicated, titration can be stopped below 200mg/day. A minimum dose of 50mg/day is necessary to continue in the study.

Table 8. Dose Adjustment Rules during Titration Phase

Cohort →	Subjects taking Phenytoin or Phenobarbital	Subjects taking AEDs other than Phenytoin or Phenobarbital
Adjustments of any Concomitant AEDs	Not Allowed	Allowed
Adjustments of YKP3089	Not Allowed	Allowed

the dose of study medication in the evening or divide the total daily dose into 2 doses. Subjects will follow the schedule of study visits and assessments detailed in [Table 1](#).

After 12 months of participation in the open-label treatment period, subjects will be re-evaluated. Those who are benefiting from treatment with YKP3089 may continue use of the drug at the discretion of the investigator, until development is stopped by SK Life Science Inc or the product is approved for marketing, or anytime at the discretion of SK Life Science Inc.

Table 9. Dose Adjustment Rules during Maintenance Phase

Cohort →	Subjects taking Phenytoin or Phenobarbital	Subjects taking AEDs other than Phenytoin or Phenobarbital
Adjustments of any Concomitant AEDs	Allowed	Allowed
Adjustments of YKP3089	Allowed	Allowed
Adjustment of Phenytoin or Phenobarbital	Allowed	Not Applicable

6.1.2.3 *Taper and follow up*

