12.5 Pharmacokinetics and Pharmacodynamics Analysis

YKP3089 plasma concentration data collected from this study will be pooled with data from other YKP3089 clinical trials for possible population pharmacokinetic and pharmacodynamic analysis. An integrated population pharmacokinetic model for YKP3089 will be developed. Standard population pharmacokinetic parameters (eg, total body clearance, CL/F) in epilepsy patients and their inter- and intra-individual variability will be estimated. The effects of demographic characteristics, concomitant medication including AEDs, laboratory values, and other subject covariates on YKP3089 pharmacokinetics will be evaluated.

For phenytoin, phenobarbital plasma concentrations obtained during titration phase (Visits 3-6) will be compared with that taken at baseline (Visit 2) to assess the effect of YKP3089 on these two AEDs. The timing of AED sampling in relation to the subject's AED dosing schedule will be factored into the analysis.

For each concomitant AED (oxcarbazepine, topiramate, lamotrigine, lacosamide, clobazam, perampanel and levetiracetam only), plasma concentrations obtained at Visits 8 and or 9 will be compared with that taken at baseline (Visit 2) to assess the effect of YKP3089 on these 7 AEDs. The timing of AED sampling in relation to the subject's AED dosing schedule will be factored into the analysis.

If warranted, the AED plasma concentration data collected from this study will be pooled with data from other YKP3089 studies to assess the potential for an interaction with YKP3089. Results will be displayed descriptively in tabular form.

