Plasma concentrations of YKP3089 and of concomitant AEDs measured in samples collected in this study will be combined with clinical data from previous studies to generate and validate population pharmacokinetic model for YKP3089. Relevant concomitant AEDs will be tested as covariates to evaluate their possible effect on YKP3089 PK. In addition, the effect of YKP3089 on the PK of relevant AEDs (like lamotrigine or lacosamide for instance) will be assessed if deemed appropriate. These analyses will be included in the separate report.

For the CSR, summary tables including descriptive statistics (mean, SD, median, minimum, maximum) for plasma concentrations of the concomitant AEDs and for plasma concentrations of the YKP3089 as per Central Lab results will be prepared by the planned collection timepoints.

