- j. At Visit 2, a single trough level of phenytoin or phenobarbital will be obtained. At visits 4, 5, 6, 7 and 8 two blood samples will be collected for the determination of phenobarbital and phenytoin plasma levels: For subjects that are taking phenytoin or phenobarbital in the morning and coming into the visits in the morning, the first blood draw will be collected upon subjects' arrival to the study unit; the second blood draw should be collected within 2 to 4 hours after the medication is taken.
- k. Concomitant AED PK draw will be done at US sites only. At Visit 2, a single trough level of concomitant AEDs will be obtained. At Visits 8 and 9, two blood samples will be collected for the determination of concomitant AED plasma levels: For subjects that are taking concomitant AEDs in the morning and coming into the visits in the morning, the first blood draw will be collected upon subjects' arrival to the study unit; the second blood draw should be collected within 30 minutes to 2 hours after the medication is taken. For patients that are taking concomitant AEDs in the afternoon and/or coming into the visits in the afternoon, the first blood draw will be collected upon subjects' arrival to the study unit; the second blood draw should be collected within 30 minutes to 2 hours after the first blood draw with timing of the dose, blood draws and strength of previous dose clearly documented. Collect at visit 8 and/ or 9 depending on stability of dosing (doses must be stable for 2 weeks prior to these visits) of concomitant AEDs and YKP3089 for subjects on concomitant AEDs other than phenytoin or phenobarbital. Concomitant AEDs levels will be obtained only for oxcarbazepine, topiramate, lamotrigine, lacosamide, clobazam, perampanel and levetiracetam.
- l. Every 6 months after Visit 14.
- m. Every 12 months after Visit 14.
- n. Sites must instruct the subject and schedule the visit accordingly to obtain a trough level. Also the blood must be collected before first dose of YKP3089.
- o. If a CT or MRI has not been performed within the last 10 years, one must be performed prior to Visit 2. If an EEG report cannot be obtained, and the subject is otherwise eligible, an EEG may be performed
- p. At visit 1, 14, and yearly thereafter, full physical. At visit 3-10, limited physical exam to identify evidence of hypersensitivity signs such as rash, swelling, lymphadenopathy and fever.

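### For the seven other AEDs, the Visit 8/9 versus Visit 2 comparison takes no account of AED dose, although doses may change in between, so a dose change can mimic or hide a YKP3089 interaction in either direction

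*Protocol*

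**What the plan says.** Objective 4 in the Protocol Synopsis is "Population pharmacokinetics of YKP3089 and concomitant AEDs". The drugs concerned here are oxcarbazepine, topiramate, lamotrigine, lacosamide, clobazam, perampanel and levetiracetam. They are sampled at US sites only, in subjects not taking phenytoin or phenobarbital (Protocol 9.4 and Table 11).

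- **Comparison.** Protocol 12.5 states for each drug that "plasma concentrations obtained at Visits 8 and or 9 will be compared with that taken at baseline (Visit 2) to assess the effect of YKP3089". The one adjustment it names is this: "The timing of AED sampling in relation to the subject's AED dosing schedule will be factored into the analysis".
- **Dose changes in between.** For this cohort Protocol 6.1.2.1 says of the titration phase: "The investigator may add, remove, or adjust the dosage of any concomitant AEDs, as clinically indicated". Protocol Table 8 and SAP Table 3 agree. In the phenytoin/phenobarbital cohort, by contrast, the total daily dose of every other AED is held fixed during titration.
- **Stability rule.** The later samples are taken "depending on stability of dosing (doses must be stable for 2 weeks prior to these visits) of concomitant AEDs and YKP3089" (SAP Appendix 1, footnote k; Protocol 9.4 and SAP 12 say the same). Nothing requires the dose at that time to equal the Visit 2 dose.
- **SAP analysis.** SAP 12 gives descriptive statistics of concentrations by planned timepoint. Beyond that, "the effect of YKP3089 on the PK of relevant AEDs (like lamotrigine or lacosamide for instance) will be assessed if deemed appropriate", in a separate report. SAP 11.4.2 derives dose changes visit by visit for phenytoin and phenobarbital, with no counterpart for the seven AEDs.

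**The concern.** Protocol 12.5 gives the comparison a causal purpose: the difference between the two times is to be read as the effect of YKP3089. A concentration depends on the AED dose as well as on any interaction. If the dose has moved since Visit 2, the contrast mixes the two. Two weeks of stable dosing helps bring the later sample near steady state at the current dose, but it does not make that dose the baseline dose. A reader of the clinical study report could take a dose effect for an interaction, or miss an interaction that a dose change has offset.

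**Working it through.** The plan states no sample size, power or interaction size for these AEDs, so there is no figure to reproduce. Two checks apply.

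**1. How much of the interval the stability rule covers**

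Inputs: Visit 2 is Day 1, Visit 8 is Day 85 and Visit 9 is Day 99 (Protocol 9.1). The look-back is 14 days (Protocol 9.4).

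- Visit 8: 85 − 1 = 84 days; 84 − 14 = 70 uncovered; 70/84 = 83%.
- Visit 9: 99 − 1 = 98 days; 98 − 14 = 84 uncovered; 84/98 = 86%.

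Most of the titration phase, in which AED changes are allowed, lies outside the rule.

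**2. What a dose change does to the ratio**

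Assume concentration is proportional to dose. For one subject, observed ratio = I × d, where I is the true interaction ratio and d is the later AED dose divided by the Visit 2 dose.

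If a share f of subjects has a mean dose cut c, unrelated to their own I, the mean ratio is I × (1 − f × c). For a mean increase g it is I × (1 + f × g). The documents give none of f, c, g or I. The values below are assumptions, shown as a range.

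| Change | Factor | I = 1.00 | I = 1.25 | I = 0.75 |
|---|---|---|---|---|
| 25% cut in 10% | 1 − 0.10 × 0.25 = 0.975 | 0.975 | 1.219 | 0.731 |
| 50% cut in 40% | 1 − 0.40 × 0.50 = 0.80 | 0.80 | 1.00 | 0.60 |
| 25% increase in 10% | 1 + 0.10 × 0.25 = 1.025 | 1.025 | 1.281 | 0.769 |
| 50% increase in 40% | 1 + 0.40 × 0.50 = 1.20 | 1.20 | 1.50 | 0.90 |

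The I = 1.00 column shows mimicry. The I = 1.25 column shows hiding by cuts and exaggeration by increases; the I = 0.75 column shows the reverse.

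On the geometric scale the factor is d^f. The same four cases give 0.75^0.10 = 0.972, 0.50^0.40 = 0.758, 1.25^0.10 = 1.023 and 1.50^0.40 = 1.176. If few doses change the effect is small: halving the dose in 10% of subjects gives 0.50^0.10 = 0.933, a shift of about 7%.

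**After dose normalisation.** Dividing each concentration by the total daily dose at that time gives (I × d)/d = I, whatever f, c or g are, provided kinetics are dose-proportional.

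**The case against.** The strongest reply is that population PK, not the simple comparison, carries objective 4. Protocol 6.2.1 assigns concomitant AED exposure to a population approach, and SAP 7.1 places the results in a separate report. Dose, date and time before each draw are recorded (Protocol 9.4), so such a model could condition on dose. SAP 11.4 also lists concomitant AED exposure by subject and visit, and SAP 10.1 rules out inference. It stands that no data are lost and that objective 4 as worded contains no error. But SAP 12 makes the model of YKP3089's effect on AEDs conditional and gives no rule for dose. A by-subject listing does not correct a summary table, and a descriptive ratio can be confounded as readily as a tested one.

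A reader might infer that the bias runs towards no interaction, because somnolence, dizziness, fatigue and gait disorder (Protocol 4.4.3) would prompt AED cuts. The documents do not support a direction. Those events are reported for the YKP3089 group, not as AED toxicity. In this cohort YKP3089 itself may be adjusted, and AED increases are allowed in subjects enrolled with uncontrolled seizures.

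A reader might also infer that restricting the analysis to subjects with an unchanged dose removes the problem. That restriction selects on a post-baseline event. If doses are cut where levels rise, it drops the subjects with the largest interaction.

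**Conclusion.** The point holds as a fault in the planned analysis that should be corrected. Followed as written, the Visit 8/9 to Visit 2 contrast for the seven AEDs cannot separate a YKP3089 effect from a change in AED dose, and the error can go either way.

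Its size is unknown. The factors of 0.975-0.80 for cuts and 1.025-1.20 for increases illustrate assumed rates. They rest on dose proportionality and on dose changes being unrelated to each subject's own interaction. It would go too far to say that the plan will hide an interaction of a given size: taking a true 1.25 down to 1.00 needs a mean 50% cut in 40% of subjects with no offsetting increases.

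The point may be weaker for clobazam. Protocol 7.3, criterion 6, requires qualifying benzodiazepines to stay unchanged throughout the study, whereas Protocol 6.1.2.1 and Table 8 allow any concomitant AED to be adjusted. If clobazam falls under the benzodiazepine rule, these passages must be reconciled.

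**What to change.** In Protocol 12.5 and SAP 12, for each of the seven AEDs:

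1. Make the main summary the within-subject ratio, Visit 8/9 to Visit 2, of concentration divided by the total daily dose of that AED, in all subjects sampled at both times. Use the pre-dose (arrival) sample at Visit 8/9 where available, to match the Visit 2 trough.
2. Give the same ratio in subjects with an unchanged dose of that AED as a sensitivity analysis only, with a note that it selects on a post-baseline event.
3. Report the number of subjects whose dose of that AED increased, decreased or did not change between the two samples.
4. Keep the summaries descriptive, in line with SAP 10.1: n, geometric mean ratio and a measure of spread.

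No new data or visits are needed and clinical management does not change. SAP 4 allows revision before database lock. The cost is SAP wording and a few derived variables. Two limits remain and should be stated: dose normalisation assumes approximate dose proportionality, and it does not correct for another AED being added or removed between the samples.
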